### 8.4.3 CLASSIFICATION OF AN ADVERSE EVENT

#### 8.4.3.1 SEVERITY OF EVENT

For adverse events (AEs) not included in the protocol defined grading system, the following guidelines will be used to describe severity.

- **0 – No AE**
- **1 - Mild AE** – Events require minimal or no treatment and do not interfere with the participant's daily activities.

- **2 – Moderate AE** – Events result in a low level of inconvenience or concern with the therapeutic measures. Moderate events may cause some interference with functioning.
- **3 – Severe AE** – Events interrupt a participant’s usual daily activity and may require systemic drug therapy or other treatment. Severe events are usually potentially life-threatening or incapacitating. Of note, the term “severe” does not necessarily equate too “serious”.
- **4** – Life threatening or disabling AE
- **5** – Fatal AE

#### 8.4.3.2 RELATIONSHIP TO STUDY INTERVENTION/EXPERIMENTAL MANIPULATION

All adverse events (AEs) will have their relationship to study procedures, including the intervention, assessed by an appropriately trained clinician based on temporal relationship and his/her clinical judgment. The degree of certainty about causality will be graded using the categories below.

- **Definitely Related** – There is clear evidence to suggest a causal relationship, and other possible contributing factors can be ruled out. The clinical event, including an abnormal laboratory test result, occurs in a plausible time relationship to study procedures administration and cannot be explained by concurrent disease or other drugs or chemicals. The response to withdrawal of the study procedures should be clinically plausible. The event must be pharmacologically or phenomenologically definitive.
- **Probably Related** – There is evidence to suggest a causal relationship, and the influence of other factors is unlikely. The clinical event, including an abnormal laboratory test result, occurs within a reasonable time after administration of the study procedures, is unlikely to be attributed to concurrent disease or other drugs or chemicals, and follows a clinically reasonable response on withdrawal.
- **Potentially Related** – There is some evidence to suggest a causal relationship (e.g., the event occurred within a reasonable time after administration of study procedures). However, other factors may have contributed to the event (e.g., the participant’s clinical condition, other concomitant events). Although an AE may rate only as “possibly related” soon after discovery, it can be flagged as requiring more information and later be upgraded to “probably related” or “definitely related”, as appropriate.
- **Unlikely to be related** – A clinical event, including an abnormal laboratory test result, whose temporal relationship to study procedures administration makes a causal relationship improbable (e.g., the event did not occur within a reasonable time after administration of the study procedures) and in which other drugs or chemicals or underlying disease provides plausible explanations (e.g., the participant’s clinical condition, other concomitant treatments).
- **Not Related** – The AE is completely independent of study procedures administration, and/or evidence exists that the event is definitely related to another etiology. There must be an alternative, definitive etiology documented by the clinician.

#### 8.4.3.3 EXPECTEDNESS

A clinician with appropriate expertise in chronic pelvic pain will be responsible for determining whether an adverse event (AE) is expected or unexpected. An AE will be considered unexpected if the nature,

severity, or frequency of the event is not consistent with the risk information previously described for the study procedures.

---

#### 8.4.4 TIME PERIOD AND FREQUENCY FOR EVENT ASSESSMENT AND FOLLOW-UP

The occurrence of an adverse event (AE) or serious adverse event (SAE) may come to the attention of study personnel during study visits and interviews of a study participant presenting for medical care, or upon review by a study monitor.

All AEs, not otherwise precluded per the protocol, will be captured on the appropriate case report form (CRF). Information to be collected includes event description, time of onset, clinician's assessment of severity, relationship to study procedures (assessed only by those with the training and authority to make a diagnosis), and time of resolution/stabilization of the event. All AEs occurring while on study will be documented appropriately regardless of relationship. All AEs will be followed to adequate resolution.

Any medical or psychiatric condition that is present at the time that the participant is screened will be considered as baseline and not reported as an AE. However, if the study participant's condition deteriorates at any time during the study, it will be recorded as an AE.

Changes in the severity of an AE will be documented to allow an assessment of the duration of the event at each level of severity to be performed. Documentation of onset and duration of each episode will be maintained for AEs characterized as intermittent.

Study coordinator will record events with start dates occurring any time after informed consent is obtained until 7 (for non-serious AEs) or 30 days (for SAEs) after the last day of study participation. At each study visit, the investigator will inquire about the occurrence of AE/SAEs since the last visit. We will primarily rely on patient self-report of adverse events and will not proactively search internal or external medical record systems to identify these. Events will be followed for outcome information until resolution or stabilization.

---

#### 8.4.5 ADVERSE EVENT REPORTING

AEs will be reported to the University of Michigan IRBMED as required and to NIH annually.

---

#### 8.4.6 SERIOUS ADVERSE EVENT REPORTING

In consultation with the PI, a trained member of the study team will be responsible for conducting an evaluation of a serious adverse event and shall report the results of such evaluation to NIH and the

reviewing Institutional Review Board (IRB) as soon as possible, but in no event later than 10 working days after the investigator first learns of the event.

---

#### 8.4.7 REPORTING EVENTS TO PARTICIPANTS

Serious adverse events that have been deemed probably or definitely related to the intervention will be reported to patients within 60 days of the incident. All other adverse events, serious adverse events, and incidental findings will be communicated to participants along with study-related results by email or preferred method of communication within one year following the end of the study.

### 8.5 UNANTICIPATED PROBLEMS

---

#### 8.5.1 DEFINITION OF UNANTICIPATED PROBLEMS

This protocol uses the definition of Unanticipated Problems as defined by the Office for Human Research Protections (OHRP). OHRP considers unanticipated problems involving risks to participants or others to include, in general, any incident, experience, or outcome that meets all of the following criteria:

- Unexpected in terms of nature, severity, or frequency given (a) the research procedures that are described in the protocol-related documents, such as the Institutional Review Board (IRB)-approved research protocol and informed consent document; and (b) the characteristics of the participant population being studied;
- Related or possibly related to participation in the research (“possibly related” means there is a reasonable possibility that the incident, experience, or outcome may have been caused by the procedures involved in the research); and
- Suggests that the research places participants or others at a greater risk of harm (including physical, psychological, economic, or social harm) than was previously known or recognized.

---

#### 8.5.2 UNANTICIPATED PROBLEMS REPORTING

The investigator will report unanticipated problems (UPs) to the reviewing Institutional Review Board (IRB). The UP report will include the following information:

- Protocol identifying information: protocol title and number, PI’s name, and the IRB project number
- A detailed description of the event, incident, experience, or outcome
- An explanation of the basis for determining that the event, incident, experience, or outcome represents an UP
- A description of any changes to the protocol or other corrective actions that have been taken or are proposed in response to the UP

To satisfy the requirement for prompt reporting, UPs will be reported using the following timeline:

- UPs that are serious adverse events (SAEs) will be reported to the IRB and to NIH as soon as possible, but in no event later than 10 working days after the investigator first learns of the event.
- Any other UP will be reported to the IRB and NIH annually.
- All UPs should be reported to appropriate institutional officials (as required by an institution's written reporting procedures), the supporting agency head (or designee), and the Office for Human Research Protections (OHRP) annually.

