## 2.3 RISK/BENEFIT ASSESSMENT

### 2.3.1 KNOWN POTENTIAL RISKS

*Breach of confidentiality:* Participation in this study poses a risk for breach of confidentiality. Several measures have been taken to reduce the risk of breach of confidentiality. These include training of study team members, electronic and physical security measures for data capture and storage and collecting a minimum of identifiable information for each individual project. Breach of confidentiality will be considered a “definitely related” Serious Adverse Event. As such, it will be reported to the University of Michigan IRB within 7 days of occurrence, and a remediation plan will be put in place immediately.

*Discomfort associated with being asked personal questions about health history and the completion of questionnaires:* Any participant becoming distressed while completing questionnaires will be encouraged to seek clarification of any questions that they find to be unclear or troubling. All participants are told that they have the option to terminate participation without penalty and/or will be assisted in arranging medical/ psychiatric help including, if necessary, emergency treatment if needed.

*Symptom exacerbation:* We do not anticipate that the *My Pelvic Plan* program is likely to place patients at an increased risk of symptom exacerbations. Cognitive and behavioral programs have been shown to be low risk for adverse events. However, we will discuss that new activities, such as physical therapy and exercise, sometimes precipitate a temporary increase in myofascial pain, and will offer basic anticipatory guidance. This is a well-described phenomenon and is not unique to this program. Our CPP provider have extensive expertise in determining whether exacerbations are typical given possible triggers and can offer individual guidance on whether additional evaluation is warranted.

During the study period, all patients will receive usual care as determined by their CPP provider and PCP. While we will not enroll patients who are planning to undergo surgery during the study period, patients will be able to proceed with any intervention determined to be necessary by their medical providers, including surgery and medication changes, without being excluded from our analysis. We will collect data on interim surgery or medication changes at the 3 and 6-month follow up periods.

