### 8.4.2 DEFINITION OF SERIOUS ADVERSE EVENTS

We will consider the following to be serious adverse events:

- Pain exacerbation prompting inpatient hospitalization
- Pain exacerbation prompting urgent or emergent surgical evaluation
- Suicide attempt or significant deterioration of psychiatric conditions resulting in inpatient psychiatric hospitalization

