### 8.5.3 REPORTING UNANTICIPATED PROBLEMS TO PARTICIPANTS

Unanticipated problems will be reported to participants along with adverse events, serious adverse events, incidental findings and study-related results by email or preferred method of communication within one year following the end of the study.

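### Unanticipated problems that are not SAEs go to the IRB and NIH only annually, under a timeline meant to be prompt, and two related reporting rules do not match

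*Combined protocol and SAP*

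**What the plan says.** All references are to the combined protocol and SAP.

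**Reports to the IRB and NIH.** Section 8.5.2 introduces its timeline as meeting the requirement for prompt reporting. Unanticipated problems that are SAEs are due within 10 working days of the investigator learning of them. For the rest: "Any other UP will be reported to the IRB and NIH annually". Section 8.5.1 requires an unanticipated problem to be unexpected, at least possibly related to the research, and a sign of greater risk than was recognised before.

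**Breach of confidentiality.** Section 2.3.1 says: "Breach of confidentiality will be considered a “definitely related” Serious Adverse Event", and adds that "it will be reported to the University of Michigan IRB within 7 days of occurrence". Section 8.4.2 opens its list with "We will consider the following to be serious adverse events" and gives three clinical or psychiatric items; a breach is not among them. Section 8.4.6 sends SAE evaluations to NIH and the IRB as soon as possible and "in no event later than 10 working days after the investigator first learns of the event".

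**Notice to participants.** Under 8.4.7, SAEs judged probably or definitely related to the intervention "will be reported to patients within 60 days of the incident"; all other events are communicated within one year after the study ends. Section 8.5.3 says "Unanticipated problems will be reported to participants along with adverse events" and study results, also within one year after the end, and makes no exception.

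**The concern.** The annual rule defeats the purpose stated just above it. A non-SAE unanticipated problem is, by the protocol's own definition, new information about risk, and patients who join before it is reported consent on the old risk statement. Section 10.1.9 gives protocol deviations a limit of 30 working days from identification, so a deviation has a tighter clock than a newly recognised risk.

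The IRB and NIH also carry much of the outside oversight here. Safety is watched by the principal investigator and the primary mentor (10.1.5), and safety analyses, interim analyses and clinical monitoring are all marked not applicable (9.4.4, 9.4.6, 10.1.6).

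The other two mismatches are smaller. A coordinator handling a breach finds two deadlines with different starting points, and an SAE list that omits the event. For an event that is both an unanticipated problem and a related SAE, 8.4.7 and 8.5.3 give different dates for telling participants.

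**Working it through.** The plan states no figure of its own on this point, so there is nothing to reproduce. The check sets the rules side by side and then sizes the annual rule by accrual.

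**1. Rules compared**

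- Unanticipated problem that is an SAE, to IRB and NIH: 10 working days from first knowledge (8.5.2).
- Any other unanticipated problem, to IRB and NIH: annually (8.5.2).
- Breach, to IRB: 7 days from occurrence (2.3.1).
- SAE, to IRB and NIH: 10 working days from first knowledge (8.4.6).
- Probably or definitely related SAE, to participants: 60 days from the incident (8.4.7).
- Unanticipated problem, to participants: within one year after study end (8.5.3).

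The first two lines are tiers by event type and do not contradict each other. The fault in the second is that it does not fit the stated aim. The third and fourth lines differ in length and in starting point, and 8.4.2 leaves the class of a breach unsettled. The fifth and sixth lines conflict for an event that meets both descriptions.

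**2. Size of the annual rule**

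Inputs: 69 participants over 18 months (8.2). Assumption: even accrual.

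- Rate: 69 / 18 = 3.83 per month.
- Enrolled during a delay = 3.83 × delay in months.
- Worst case, problem just after an annual report: 69 / 18 × 12 = 46; 46 / 69 = 67%.
- Average wait under annual reporting, 6 months: 69 / 18 × 6 = 23; 23 / 69 = 33%.
- For comparison, 10 working days is 14 calendar days, or 14 / 30.4 = 0.46 months: 3.83 × 0.46 = 1.8 patients (3%).

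These figures take the whole wait to fall within the enrolment period.

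**3. Sensitivity**

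- If accrual took 24 months, the worst case is 12 / 24 = 50%; if 30 months, 12 / 30 = 40%.
- If annual reports fell at months 12 and 24 (an assumption; the protocol gives no dates), the share enrolled between a problem at month t (before month 12) and its report is (12 − t) / 18. This exceeds one half only when t < 3, that is, in the first 3 of the 18 months.

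**4. Size of the participant mismatch**

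The study ends when the last 6-month questionnaires are in (4.1, 8.2). That is about 18 + 6 = 24 months after first enrolment, or 18 + 7 = 25 using the 7-month participant duration in the synopsis. Adding the one-year allowance gives 36 to 37 months for an event at first enrolment, against 60 days under 8.4.7.

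**The case against.** The strongest reply is that most of these limits are deliberate tiers in a low-risk, 69-patient web study, and that other provisions soften the annual rule. Adverse events go to the IRB as required (8.4.5), so a problem that is also an adverse event may fall under an earlier deadline in IRB policy that the documents do not show. Unexpected or unacceptable risk is a ground for suspension, with prompt notice to participants, the IRB and NIH (10.1.1). Protocol and consent changes need IRB approval first (Statement of Compliance). The two breach deadlines can also both be met by using the earlier date, provided the breach is found in time.

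The point about tiers stands. The safeguards are real but partial: none sets a clock for a non-SAE unanticipated problem, and suspension is discretionary. Using the earlier date does not help when a breach is discovered more than 7 days after it happened.

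A reader might infer three stronger things that the documents do not support:

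- **That a breach could go unreported to the IRB for a year.** Section 2.3.1 expressly classes it as an SAE with a 7-day limit. It is also a disclosed risk, so it may not meet the unexpectedness test in 8.5.1.
- **That many related SAEs would already be past the 60-day limit when the team learns of them.** That assumes first report at the 3-month questionnaire. The Schedule of Activities marks adverse event reporting at every month without limiting it to one arm. The nominal lag is about 30 days, and with both 14-day windows at their extremes it is 30 + 14 + 14 = 58 days.
- **That study end, for the participant notice, is the end of the 3-year study duration.** Sections 4.1 and 8.2 tie it to the last 6-month questionnaires.

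**Conclusion.** The point holds, centred on the annual rule in 8.5.2. It lets new risk information stay from the IRB and NIH for up to 12 months, during which 46 of 69 patients (67%) could enrol at worst and about 23 (33%) at the average wait. Both figures rest on even accrual over the planned 18 months, and the share falls if accrual is slower or the problem arises late in enrolment.

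The breach rules (2.3.1, 8.4.2, 8.4.6) and the participant-notice rules (8.4.7, 8.5.3) are separate inconsistencies that need reconciling. A reader might infer that these clashes cause the long delay to the IRB. They do not: a breach or an SAE-type problem still reaches the IRB within about one to two weeks, counted from occurrence or awareness according to the section, which is 1 to 2 enrolments. The delay comes from the annual rule alone.

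The sponsor should correct this. It concerns safety reporting and does not affect the statistical analysis.

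**What to change.** 1. In 8.5.2, replace the annual interval for reporting non-SAE unanticipated problems to the IRB and NIH with the limit already used there for SAE-type problems: 10 working days from the investigator's first knowledge.
2. Give breach of confidentiality one class and one IRB deadline, running from awareness, and state it identically in 2.3.1, 8.4.2 and 8.4.6.
3. In 8.5.3, add an exception for events already covered by the 60-day participant notice in 8.4.7.

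The first and third changes reuse time limits that the protocol already contains. The cost is rewording in these sections and a few extra short reports to the IRB and NIH. Study procedures, the sample size and the analysis are unchanged.

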### 8.5.3 REPORTING UNANTICIPATED PROBLEMS TO PARTICIPANTS

Unanticipated problems will be reported to participants along with adverse events, serious adverse events, incidental findings and study-related results by email or preferred method of communication within one year following the end of the study.

## 9 STATISTICAL CONSIDERATIONS

### 9.1 STATISTICAL HYPOTHESES

- Primary Endpoint:

We hypothesize that patients who receive the *My Pelvic Plan* intervention in addition to usual care will demonstrate improvement on PROMIS Pain Interference SF 4a from baseline to 3-month follow-up. Alternatively, our null hypothesis is that there will be no difference in Pain Interference from baseline to 3-month follow up. As this is a pilot study, we will be evaluating preliminary program effectiveness by comparing the intervention group to an active control group and will use this information to generate effect size for a trial to evaluate efficacy.

- Secondary Endpoints:

We hypothesize that patients who receive the *My Pelvic Plan* intervention in addition to usual care + symptom tracker will demonstrate improvements on PROMIS Pain Intensity and PROMIS Self Efficacy for Managing Symptoms SF 4a from baseline to 3-month follow-up. Alternatively, our null hypothesis is that there will be no difference in Pain Intensity and Self-Efficacy from baseline to 3-month follow up.

### 9.2 SAMPLE SIZE DETERMINATION

As this is a pilot study, we have chosen to recruit a sample of 69 patients so that we can assess the feasibility of the project and to derive important effect size estimates for the definitive clinical trial that

will be conducted in a future R01 application. We are not attempting to power the analyses to detect a difference in our primary outcome (pain interference).

In addition to pain interference, we will also examine pain intensity and health-related self-efficacy to assess whether these outcomes might be more appropriate primary outcomes in an efficacy trial.

### 9.3 POPULATIONS FOR ANALYSES

We will use an intent to treat analysis. Primary outcome (pain interference) will be assessed at 3-months and 6-month data will only contribute to secondary outcomes. Given this, we will plan carry the last observation forward (either 3-month or baseline) for patients who are lost to follow up at 6-months.

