### 5.4 STRATEGIES FOR RECRUITMENT AND RETENTION

We will be using thoughtful recruitment and allocation methods to minimize bias. We will attempt to include a diverse group of participants for this study, with intentional recruitment to reflect diversity in age, race, geographic location and pelvic pain conditions.

We will contact both intervention and control patients with text or email prompts to visit their respective website on prespecified basis with goal of increasing program utilization and study retention. In the first 12 weeks of the study (active phase), participants will receive a weekly text or email prompt directing them to a specific module or portion of their respective website. During the remaining time in the study (maintenance phase), all participants will receive monthly text or email prompts to visit their respective website. Details of the prompts for the intervention and control groups are included in 8.2 Study evaluation and procedures.

We are unable to track website utilization for specific users. However, we will send an email link to a survey once per month which will ask which skills (from the *Managing Symptoms* section of the website) they used in the last month regardless of whether they visited that module in the site. We assume that some patients will need repeated exposure to skills to gain mastery and incorporate into their routine, whereas other patients may visit a module once and be able to incorporate it into regular practice.

Patients will receive a questionnaire battery at 3-month interval (primary endpoint) and 6-month interval (secondary endpoint). Patients will receive a reminder email if they have not completed the survey or questionnaire within 4 days, 7 days, and 14 days. Only three reminders will be sent per survey/questionnaire, with the exception of the 6-month survey, for which patients may receive one additional reminder at 21 days.

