### 7.3 LOST TO FOLLOW-UP

Patients will receive an email with a link to questionnaires and utilizations surveys at each time point specified above. If questionnaires are not completed within 4 days, an automatic reminder email will be

sent. If questionnaires are not completed within 7 days, a study member will call with a reminder. If questionnaire is not completed with 14 days, a study member will call with another reminder. Patient will be considered lost to follow up if they fail to complete the 6-month questionnaire within 21 days after survey invitation.

We will not exclude or dismiss patients based on completion of 6-month questionnaire or monthly utilization survey as these are not essential for the primary outcome.

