#### 9.4.2 ANALYSIS OF THE PRIMARY ENDPOINT(S)

The primary outcome (PROMIS Pain Interference) is a continuous measure and utilizes a standardized, publicly available scoring system. We will report mean and standard deviation for each group.

Given pilot RCT design, we will use a simple posttreatment comparison of pain interference at 3-months. We will compare means with t-test. All tests will be two-sided at 5% significance level. Of note, data collected at 6-month interval will be analyzed as an exploratory outcome.

We will estimate effect size by calculating Hedges'  $g$  (rather than Cohen's  $d$  because groups are different sizes) for pain interference at 3-months, which we will use in planning for future efficacy trial.

As part of our exploratory analyses, we plan to categorize patients as "responders" vs "non-responders." "Responder" will be defined as an improvement of at least 2.5 on PROMIS Pain Interference from baseline to 3-months. We will compare differences in contributing pain conditions, pain characteristics such as Fibromyalgia Survey Score or PainDETECT, and comorbid mental health factors that may be associated responder status. We tentatively plan to use logistic regression to compare factors associated with responder status. We will use these exploratory analyses to inform structure of our future efficacy trial.

We will be using an intent to treat analysis. Patients may elect to skip questions on the questionnaire and therefore it is possible that we encounter some missing data or incomplete questionnaires. We will report the proportion of missing outcome per group and characteristics of patients with missing data. If we encounter more than 5% missing data, we plan to conduct sensitivity analyses to assess effect of missingness on results.

---

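### Carrying the 3-month or baseline score forward generally biases the secondary/exploratory 6-month comparison in an unpredictable direction, and no missing-data rule is given at 3 months

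*Combined protocol and SAP*

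**What the plan says.** All references are to the combined protocol and SAP.

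- **Principle.** Section 9.3: "We will use an intent to treat analysis".
- **6 months.** The same section says "6-month data will only contribute to secondary outcomes" and, on that ground, "we will plan carry the last observation forward (either 3-month or baseline) for patients who are lost to follow up at 6-months". Sections 9.4.2 and 9.4.3 call the 6-month data exploratory.
- **3 months.** Section 9.4.2: "we will use a simple posttreatment comparison of pain interference at 3-months. We will compare means with t-test". It states no rule for a patient with no 3-month score. Section 9.4.3 plans a post-treatment comparison for the secondary outcomes, also without such a rule.
- **Missing data.** Sections 9.4.2 and 9.4.3 promise "We will report the proportion of missing outcome per group and characteristics of patients with missing data" and add: "If we encounter more than 5% missing data, we plan to conduct sensitivity analyses to assess effect of missingness on results". No method is named and no expected loss rate is given.
- **Definition of loss.** Section 7.3, repeated in section 8.2: "Patient will be considered lost to follow up if they fail to complete the 6-month questionnaire within 21 days after survey invitation". For that same questionnaire, section 5.4 says "patients may receive one additional reminder at 21 days".

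**The concern.** Carry-forward treats a patient's score as frozen at the last value. If that value is the baseline score, the patient is recorded as having changed by exactly zero. If it is the 3-month score, anything that happens between months 3 and 6 is ignored. Neither assumption is argued for in the plan. The reason offered is that the 6-month data matter less, which limits the damage but does not justify the method.

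The two visits would also rest on different patients under one intent-to-treat label. At stake is whether the 6-month estimate, listed as a timepoint for every outcome in section 3, can be trusted as an indication of durability when the next trial is planned.

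**Working it through.** **Inputs from the documents.** 69 patients at 2:1, so 46 and 23 (sections 9.2 and 6.3). Minimally important difference 2.5 points (section 9.4.9). There is no stated power, loss rate, SD or trajectory, and so no figure of the plan's to reproduce.

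**Assumptions.** Everything else below is assumed: loss rates, share of lost patients with no 3-month score, trajectories, SD 7 or 8, and visit correlation 0.6.

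**Formula.** Count improvement as positive. In one arm let d be the share missing at 6 months, b the share of those also missing at 3 months, and c3 and c6 the mean improvements. If loss is at random within arm:

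- carried-forward mean = (1−d)·c6 + d·(1−b)·c3, because a baseline-carried patient contributes zero;
- error in that arm = d·[(1−b)·c3 − c6];
- bias of the comparison = intervention error − control error.

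Worked example (effect wanes, 30% v 10% lost, all 3-month scores present): intervention 0.7×2.5 + 0.3×5 = 3.25; control 0. The estimate is 3.25 against a true 2.5, a bias of +0.75.

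| Case | Lost, int/ctl | Baseline-carried share | Int c3, c6 | Ctl c3, c6 | True | Carry-forward | Bias |
|---|---|---|---|---|---|---|---|
| Effect held | 20/20% | none | 5, 5 | 0, 0 | 5.0 | 5.0 | 0 |
| Effect held | 20/20% | 1/2 | 5, 5 | 0, 0 | 5.0 | 4.5 | −0.5 |
| Effect grows | 20/20% | 1/2 | 2.5, 5 | 0, 0 | 5.0 | 4.25 | −0.75 |
| Effect wanes | 20/20% | none | 5, 2.5 | 0, 0 | 2.5 | 3.0 | +0.5 |
| Effect wanes | 30/10% | none | 5, 2.5 | 0, 0 | 2.5 | 3.25 | +0.75 |
| Effect wanes | 20/20% | 1/2 | 5, 2.5 | 0, 0 | 2.5 | 2.5 | 0 |
| No effect | 30/10% | 1/2 | 2.5, 2.5 | 2.5, 2.5 | 0 | −0.25 | −0.25 |
| No effect | 10/30% | 1/2 | 2.5, 2.5 | 2.5, 2.5 | 0 | +0.25 | +0.25 |
| Held, both arms improve 2 | 15/15% | 2/3 | 4.5, 4.5 | 2, 2 | 2.5 | 2.25 | −0.25 |
| Held, both arms improve 2 | 30/15% | 2/3 | 4.5, 4.5 | 2, 2 | 2.5 | 1.8 | −0.7 |
| Held, both arms improve 4 | 30/15% | 2/3 | 6.5, 6.5 | 4, 4 | 2.5 | 1.6 | −0.9 |

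**Simulation, loss at random.** Runs at 46:23 with SD 7 gave 1.79, 1.59 and 2.29 for the 1.8, 1.6 and 2.25 entries.

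**Simulation, loss depending on baseline.** With the effect held at 5, base loss rates of 30% and 10%, half of the lost baseline-carried and SD 8, carry-forward understated the benefit by 0.94. An available-case comparison of 6-month scores overstated it by 0.62. Simply dropping the missing patients is therefore not a full remedy.

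**Against sampling error.** With SD 7 and no loss, the standard error is 7×√(1/46 + 1/23) = 1.79. Coverage of the 95% interval under carry-forward stayed between 93.5% and 95.8% in the runs made.

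**The two visits side by side.** A t-test on 3-month scores with no imputation can use only patients who have one. A patient with baseline only is therefore absent at 3 months. At 6 months the same patient meets the section 7.3 definition of loss, receives the baseline score and is counted.

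**The safeguard.** 5% of 69 is 3.45, so, counting patients with a missing score, the unnamed sensitivity analyses start at four.

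**The 21-day texts.** Loss is declared when the questionnaire is not in within 21 days of invitation; the extra reminder falls at 21 days. A patient who answers that reminder may already be classed as lost.

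**The case against.** The strongest objection is reach. Carry-forward applies only to 6-month data. The primary t-test is at 3 months, and so is the Hedges' g that section 9.4.2 earmarks for planning the efficacy trial. Section 9.2 disclaims power, and no stated decision turns on the 6-month contrast. All of this stands.

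Second, the size depends on invented inputs. In the 2.5-point benefit scenarios, the falls to 1.8 and 1.6 (28% and 36%) need twice the loss in the intervention arm, sizeable general improvement and an effect held from month 3. A reader might take them as the expected attenuation; the documents support no loss rate in either arm. With 10% lost after month 3 only, and the effect held, a rerun gave 2.49 against 2.5. In the held-effect cases the bias comes from baseline-only patients, and section 7.2 says early withdrawals will be replaced where possible. That reduces the problem without removing it. Silent non-responders are not replaced, and the plan does not say how a replaced patient is analysed.

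Third, a likelihood-based model recovered 2.5 in the scenarios with random loss, but plain available cases gave 2.49 there too. That agreement alone does not show the model is needed. The case for it rests on loss that depends on earlier scores, and on using one patient set at both visits.

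Fourth, a reader might infer that the plan prescribes available cases at 3 months, or that late 6-month questionnaires will be discarded. Neither is written. The first is the consequence of silence. The second is one literal reading of sections 7.3 and 9.3 together, and no text says a returned score is thrown away.

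**Conclusion.** The point holds in limited form. Carry-forward at 6 months is generally biased, and the sign depends on whether the effect is held, grows or wanes, and on loss by arm. It therefore cannot be defended as conservative. Across the assumed cases the bias ran from +0.75 (flattering the intervention) to about −0.9 point, or 30% to 36% of the 2.5-point minimally important difference. It was zero in special cases, such as an effect held with every carried score from month 3. It is smaller than the sampling error of this trial.

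A reader might conclude that the trial's main result is compromised. It is not: carry-forward does not enter the 3-month t-test or Hedges' g. What remains is an avoidable bias in a secondary or exploratory comparison, an unstated rule at 3 months, analysis sets that differ between visits under one label, and a timing clash at day 21. These are worth correcting before the data are analysed.

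**What to change.** 1. In section 9.3, delete the carry-forward sentence. Estimate the 6-month contrast from a mixed model for repeated measures using all observed baseline, 3-month and 6-month scores of all randomised patients, with arm-by-visit means and baseline means constrained equal. Say explicitly that patients who withdrew and were replaced stay in.
2. Keep the planned 3-month t-test and Hedges' g, state which patients enter them, and report the model's 3-month contrast alongside. Both visits then have an estimate resting on the same patients.
3. In sections 9.4.2 and 9.4.3, name delta-adjusted imputation as the sensitivity analysis when more than 5% are missing.
4. Reconcile the 21-day loss definition (sections 7.3 and 8.2) with the extra reminder at 21 days (section 5.4), and check both against the ±14-day visit window in section 1.3. State that any 6-month score actually returned is analysed as observed and never replaced.
5. Use one label, secondary or exploratory, for the 6-month data.

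The cost is SAP wording and a little programming; no new data are needed. The model assumes missing at random, which the delta-adjusted analysis is there to probe.
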